Annex 1. Variables of the ISMiHealth study

| Variable name | Definition | Variable | Values | | | | |
|---------------|--|-------------|--|--|--|--|--|
| | | type | | | | | |
| DC (1 / | | | | | | | |
| | PC professional (general practitioners and nurses) | | | | | | |
| pct_name | Name of the team to which the | Qualitative | PCTs in Catalonia: | | | | |
| | professional belongs | | Equipo de Atención Primaria (EAP) Gavà-1 | | | | |
| | | | EAP Esparreguera | | | | |
| | | | EAP | | | | |
| | | | EAP Molí Nou | | | | |
| | | | EAP Gornal | | | | |
| | | | EAP Sant Andreu de la Barca | | | | |
| | | | EAP Gavà-2 | | | | |
| | | | EAP Camps Blancs | | | | |
| | | | EAP Sant Les Planes | | | | |
| | | | EAP Can Vidalet | | | | |
| | | | EAP El Castell | | | | |
| | | | EAP Florida Sud | | | | |
| | | | EAP Florida Nord | | | | |
| | | | EAP Lleida Rural Sud | | | | |
| | | | EAP Alfarràs - Almenar | | | | |
| | | | EAP Ponts | | | | |
| | | | EAP Almacelles | | | | |
| | | | EAP Artesa de Segre EAP Alcarràs | | | | |
| | | | EAP El Morell | | | | |
| | | | EAP Tàrraco | | | | |
| | | | EAP Sant Pere i Sant Pau | | | | |
| | | | EAP La Canonja/Bonavista | | | | |
| | | | EAP Constantí | | | | |
| | | | EAP Jaume I | | | | |
| | | | EAP Sant Salvador/Els Pallaresos | | | | |
| | | | EAP Torreforta | | | | |
| | | | EAP El Salou | | | | |
| | | | EAP Deltebre | | | | |
| | | | EAP Gandesa | | | | |
| | | | EAP Baix Ebre | | | | |
| | | | EAP Amposta | | | | |
| | | | EAP Sant Carles de la Ràpita | | | | |
| | | | EAP El Temple | | | | |
| | | | EAP L'Ametlla de Mar – El Perelló | | | | |
| | | | EAP Ulldecona – La Sènia | | | | |
| | | | PCTs in Andalusia: | | | | |
| | | | EAP Aguadulce Sur | | | | |
| | | | EAP Adra | | | | |
| | | | EAP El Ejido Norte | | | | |
| | | | LAF LI EJIUU NUITE | | | | |

| | | | EAP Roquetas Sur |
|-------------|---------------------------------------|--------------|--|
| | | | EAP la Mojonera |
| | | | EAP Puebla de Vícar |
| pc_hp | Type of health professional | Qualitative | General practitioner/Nurse |
| pc_category | Professional category | Qualitative | Professionals in training (residents), |
| | , | | professionals on staff (permanent), |
| | | | professionals with intermediate and |
| | | | advanced vocational training |
| pc_sex | Sex of the PC professional | Qualitative | Female/Male |
| pc_age | Age of the PC professional | Quantitative | 18-70 years old |
| Centre | , , , , , , , , , , , , , , , , , , , | | , |
| рсс | PCC where the patient is attended | Qualitative | PCCs in Catalonia: |
| , , | | | Centro de Atención Primaria (CAP) Gavà-1 |
| | | | CAP Esparreguera |
| | | | CAP Molí Nou |
| | | | CAP Gornal |
| | | | CAP Sant Andreu de la Barca |
| | | | CAP Gavà-2 |
| | | | CAP Camps Blancs |
| | | | CAP Sant Les Planes |
| | | | CAP Can Vidalet |
| | | | CAP El Castell |
| | | | CAP Florida Sud |
| | | | CAP Florida Nord |
| | | | CAP Lleida Rural Sud |
| | | | CAP Alfarràs |
| | | | CAP Almenar |
| | | | CAP Ponts |
| | | | CAP Almacelles |
| | | | CAP Artesa de Segre |
| | | | CAP Alcarràs |
| | | | CAP El Morell |
| | | | CAP Tàrraco |
| | | | CAP Sant Pere i Sant Pau |
| | | | CAP La Canonja |
| | | | CAP Bonavista |
| | | | CAP Constantí |
| | | | CAP Jaume I |
| | | | CAP Sant Salvador |
| | | | CAP Els Pallaresos |
| | | | CAP Torreforta |
| | | | CAP El Salou |
| | | | CAP Deltebre |
| | | | CAP Gandesa |
| | | | CAP Baix Ebre |
| | | | CAP Amposta |
| 1 | | | CAP Sant Carles de la Ràpita |

| | | 1 | 1 |
|--------------|--|--------------|---|
| | | | CAP El Temple |
| | | | CAP L'Ametlla de Mar |
| | | | CAP El Perelló |
| | | | CAP Ulldecona |
| | | | CAP La Sènia |
| | | | PCCs in Andalusia: |
| | | | Centro de Salud Aguadulce Sur |
| | | | Centro de Salud Adra |
| | | | Centro de Salud El Ejido Norte |
| | | | Centro de Salud Roquetas Sur |
| | | | Centro de Salud la Mojonera |
| | | | Centro de Salud Puebla de Vícar |
| region | Region where the PCC is located | Qualitative | Catalonia: Lleida/Tarragona/Terres de |
| | | | l'Ebre/Costa de Ponent |
| | | | Andalusia: Almería |
| pcc_area | Type of centre | Qualitative | Urban/Rural |
| medea | Index of socioeconomic deprivation | Quantitative | |
| illedea | for each of the participating centres | Quantitative | |
| num_hp | Number of health professionals | Quantitative | |
| - - r | working at the centre (general | | |
| | practitioners and nurses) | | |
| | | | |
| mig_density | Migration density (%) of the population assigned to each centre | Quantitative | 7.0-52.0 |
| mig_assigned | Number of migrants assigned to the PCCs participating in the study | Quantitative | |
| mig_visit | Number of migrants who visited their assigned PCCs during the intervention | Quantitative | |
| group | Arm of the intervention | Qualitative | Intervention/Control |
| Patient | | | |
| sex | Sex of the patient | Qualitative | Female/Male |
| age | Age of the patient | Quantitative | From 14 years old in Andalusia and 15 |
| | | | years old in Catalonia with no age limit in |
| | | | both sites |
| area_birth | Area of birth of the patient | Qualitative | Africa/Latin-America/Asia/Eastern Europe |
| date_entry | Date of entry to the PCC | Quantitative | MM/DD/YYYY: Up to 12/31/2024 |
| date_exit | Date of exit to the PCC | Quantitative | MM/DD/YYYY: Up to 12/31/2024 |
| visits | Number of visits to the healthcare | Quantitative | |
| | centre | | |
| | | | |

| date_visits | Date of visits to the healthcare centre | Quantitative | MM/DD/YYYY: Up to 12/31/2024 |
|-----------------|---|--------------|------------------------------|
| lab_hgb | Haemoglobin | Quantitative | |
| lab_plt | Platelets | Quantitative | |
| lab_wbc | Leucocytes | Quantitative | |
| lab_neut | Neutrophils | Quantitative | |
| lab_lym | Lymphocytes | Quantitative | |
| lab_eos | Eosinophils | Quantitative | |
| lab_crea | Creatinine | Quantitative | |
| lab_urea | Urea | Quantitative | |
| lab_ast | Aspartate aminotransferase (AST) | Quantitative | |
| lab_alt | Alanine aminotransferase (ALT) | Quantitative | |
| lab_ggt | Gamma-glutamyl transpeptidase (GGT) | Quantitative | |
| lab_bili | Bilirubin | Quantitative | |
| lab_act | Coagulation | Quantitative | |
| alert_hiv | Patients fulfilling the criteria for the screening of HIV | Qualitative | Yes/No |
| alert_syph^ | Patients fulfilling the criteria for the screening of syphilis | Qualitative | Yes/No |
| alert_hbv | Patients fulfilling the criteria for the screening of HBV | Qualitative | Yes/No |
| alert_hcv | Patients fulfilling the criteria for the screening of HCV | Qualitative | Yes/No |
| alert_activetb | Patients fulfilling the criteria for the screening of active TB | Qualitative | Yes/No |
| alert_latenttb^ | Patients fulfilling the criteria for the screening of latent TB | Qualitative | Yes/No |
| alert_chagas | Patients fulfilling the criteria for the screening of T.cruzi infection | Qualitative | Yes/No |
| alert_strongy | Patients fulfilling the criteria for the screening of S. stercoralis infection | Qualitative | Yes/No |

| alert_schisto | Patients fulfilling the criteria for the screening of Schistosoma spp . infection | Qualitative | Yes/No |
|---------------|--|--------------|--------|
| alert_intpar^ | Patients fulfilling the criteria for the screening of intestinal parasites | Qualitative | Yes/No |
| alert_fgm | Patients fulfilling the criteria for the screening of FGM | Qualitative | Yes/No |
| sero_hiv | Serologies for HIV | Qualitative | Yes/No |
| sero_syph^ | Serologies for syphilis | Qualitative | Yes/No |
| sero_hbv | Serologies for HBV | Qualitative | Yes/No |
| sero_hcv | Serologies for HCV | Qualitative | Yes/No |
| cxray | Chest radiographies for active TB | Qualitative | Yes/No |
| tst^ | TST for latent TB | Qualitative | Yes/No |
| igra^ | IGRA for latent TB | Qualitative | Yes/No |
| sero_chagas | Serologies for T.cruzi infection | Qualitative | Yes/No |
| sero_strongy | Serologies for S.stercoralis infection | Qualitative | Yes/No |
| sero_schisto | Serologies for Schistosoma spp. infection | Qualitative | Yes/No |
| stool_intpar^ | Stool samples for intestinal parasites | Qualitative | Yes/No |
| fgm | Questionnaires completed for FGM | Qualitative | Yes/No |
| dx_hiv | Diagnosis of HIV | Qualitative | Yes/No |
| cd4 | CD4 cell count | Quantitative | |
| hiv_vl | HIV viral load | Quantitative | |
| dx_syph^ | Diagnosis of syphilis | Qualitative | Yes/No |
| dx_std | Diagnosis of other sexually transmitted diseases (STDs) | Qualitative | Yes/No |
| dx_hbv | Diagnosis of HBV | Qualitative | Yes/No |
| dx_hcv | Diagnosis of HCV | Qualitative | Yes/No |
| dx_activetb | Diagnosis of active TB | Qualitative | Yes/No |
| dx_latenttb^ | Diagnosis of latent TB | Qualitative | Yes/No |
| dx_chagas | Diagnosis of T.cruzi infection | Qualitative | Yes/No |
| dx_strongy | Diagnosis of S.stercoralis infection | Qualitative | Yes/No |

| dx_schisto | Diagnosis of Schistosoma spp. infection | Qualitative | Yes/No |
|-----------------|--|--------------|---|
| dx_intpar^ | Diagnosis of intestinal parasites | Qualitative | Yes/No |
| dx_fgm | Diagnosis of FGM cases | Qualitative | Yes/No |
| referral | Referral to specialists due to a diagnosis during the intervention | Qualitative | Yes/No |
| other_dx | Other diagnoses made during the intervention (besides from the infections included in the study and FGM) | Qualitative | ICD-9 or ICD-10 |
| com_dx | Comorbidities | Qualitative | ICD-9 or ICD-10 |
| immune_dx | Immunosuppressive diagnoses during the intervention period | Qualitative | ICD-9 or ICD-10 |
| drugs | Drugs prescribed to patients during the intervention | Qualitative | Anatomical Therapeutic Chemical (ACT) codes |
| immune_drugs | Immunosuppressive drugs prescribed during the intervention period | Qualitative | ACT codes |
| doses | Prescribed drug doses | Quantitative | |
| tto_start | Treatment start date | Quantitative | MM/DD/YYYY: Up to 12/31/2024 |
| tto_end | Treatment end date | Quantitative | MM/DD/YYYY: Up to 12/31/2024 |
| cost | Cost of the prescribed drugs | Quantitative | In euros (€) |
| Hospital (MBDS) | | | |
| hosp | Hospitalisation | Qualitative | Yes/No |
| hosp_dx | Primary diagnosis | Qualitative | ICD9 or ICD-10 |
| hosp_dxother | Other diagnosis | Qualitative | ICD9 or ICD-10 |
| hosp_dates | Hospitalisation dates | Quantitative | MM/DD/YYYY: Up to 12/31/2024 |
| hosp_hgb | Haemoglobin | Quantitative | |
| hosp_plt | Platelets | Quantitative | |
| hosp_wbc | Leucocytes | Quantitative | |
| hosp_neut | Neutrophils | Quantitative | |
| hosp_lym | Lymphocytes | Quantitative | |
| hosp_eos | Eosinophils | Quantitative | |
| hosp_crea | Creatinine | Quantitative | |

| hosp_urea | Urea | Quantitative | |
|-----------------------|--|--------------|---|
| hosp_ast | AST | Quantitative | |
| hosp_alt | ALT | Quantitative | |
| hosp_ggt | GGT | Quantitative | |
| hosp_bili | Bilirubin | Quantitative | |
| hosp_act | Coagulation | Quantitative | |
| hosp_sympt | Symptoms | Qualitative | Fever, diarrhoea, rash, fatigue, ulcers, among others |
| hosp_uci | Need for an Intensive Care Unit | Qualitative | Yes/No |
| hosp_vent | Need for mechanical ventilation | Qualitative | Yes/No |
| hosp_drugs | Drugs prescribed | Qualitative | ACT codes |
| hosp_doses | Drug doses | Quantitative | |
| hosp_tto_start | Treatment start date | Quantitative | MM/DD/YYYY: Up to 12/31/2024 |
| hosp_tto_end | Treatment end date | Quantitative | MM/DD/YYYY: Up to 12/31/2024 |
| hosp_drugs_cost | Cost of the drugs | Quantitative | In euros (€) |
| hosp_cost | Cost attributed to hospitalisation | Quantitative | In euros (€) |
| Hospital follow-up (I | MBDS) | | |
| followup | Number of follow-up visits after hospitalisation | Quantitative | |
| followup_dates | Dates of follow-up visits after hospitalisation | Quantitative | MM/DD/YYYY: Up to 12/31/2024 |
| followup_dx | Diagnosis made during the follow-up visits | Qualitative | ICD9 or ICD-10 |
| followup_hgb | Haemoglobin | Quantitative | |
| followup_plt | Platelets | Quantitative | |
| followup_wbc | Leucocytes | Quantitative | |
| followup_neut | Neutrophils | Quantitative | |
| followup_lym | Lymphocytes | Quantitative | |
| followup_eos | Eosinophils | Quantitative | |
| followup_crea | Creatinine | Quantitative | |
| followup_urea | Urea | Quantitative | |

| followup_ast | AST | Quantitative | | |
|--------------------|--|--------------|------------------------------|--|
| followup_alt | ALT | Quantitative | | |
| followup_ggt | GGT | Quantitative | | |
| followup_bili | Bilirubin | Quantitative | | |
| followup_act | Coagulation | Quantitative | | |
| followup_drugs | Drugs prescribed during follow-up visits | Qualitative | ACT codes | |
| followup_doses | Drug doses | Quantitative | | |
| followup_tto_start | Treatment start date | Quantitative | MM/DD/YYYY: Up to 12/31/2024 | |
| followup_tto_end | Treatment end date | Quantitative | MM/DD/YYYY: Up to 12/31/2024 | |
| followup_cost | Cost of the drugs | Quantitative | In euros (€) | |
| Health events | | | | |
| cured | Cured patients | Qualitative | Yes/No | |
| mortality | Patients who died during the intervention period | Qualitative | Yes/No | |

PC: Primary care, PCT: Primary care team, EAP: Equipo de Atención Primaria, PCC: Primary care centre, CAP: Centro de Atención Primaria, HIV: human immunodeficiency virus, HBV: hepatitis B virus, HCV: hepatitis C virus, TB: tuberculosis, FGM: female genital mutilation, ACT: Anatomical Therapeutic Chemical, ICD-9: International Classification of Diseases Ninth Revision, ICD-10: International Classification of Diseases Tenth Revision, MBDS: Minimum basic dataset; ^Only in the Andalusian site

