Health professionals from both intervention and control centres will receive training sessions, targeting staff of the centres including nurses, medical doctors, and other technicians. The sessions will cover background information on each infection, including epidemiology, diagnostic tools, treatment available, particular aspects in high-risk groups such as immunosuppressed patients, data on cost-effectiveness, and screening recommendations for migrants.

Participants' selection

Therefore, when an individual comes to the PCC for any reason, the health professional will receive a message, in the EPR system, inserted as a pending task assignment with a recommendation on the diseases that should be considered for screening, based on this person's background characteristics. The tool is also able to identify if a person had already a diagnosis of any of the conditions included in the algorithm (based on ICD-10, International Classification Diagnosis codes) or if a diagnostic test had been performed for any condition included in the program. In such cases, the automated electronic prompt does not appear for that condition. A pilot test will be conducted with 3 health professionals to assure the correct functioning of the tool. In the control centres, we will hold just training sessions with the same screening recommendations as for the intervention centres but will not initiate the tool/prompts onto the EPR system. When the patient comes to the PCC, health professionals will decide what diseases/conditions should be screened for according to the information received either through the digital software (intervention centres) or based on their knowledge on the epidemiological background of the diseases (control centres), which was included in the training programme. In any case, health professionals will be responsible for requesting a blood test or a chest radiography and/or the derivation to a specialist.

Participant's selection for the feasibility and acceptability evaluation (focus group discussions, IDIs and survey)

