For the survey of the programme acceptance, a list of possible candidates (sex and gender balanced) will be made for both groups, health professionals and migrant patients. The same member of the PCC leadership team that sent the invite to the GP and nurses for the FGs of the 6 participating PCCs will send an anonymous questionnaire via email or WhatsApp, using the secured LimeSurvey platform, to the chosen health professionals and migrant patients. Candidates will receive the invitation by email or message with a link to the anonymous survey and their access to it will represent their consent to participate.

6. STUDY PROCEDURES, TREATMENT AND CALENDAR OF THE STUDY.

In line with the existing national guidelines, active TB will be screened with chest radiography. If radiographic findings are compatible with TB, or if TB symptoms are present, the person should be immediately referred to a specialist for full diagnostic workup. For HIV testing, a standard HIV ELISA test will be performed. For HBV, the Australian antigen (HBsAg) and the IgG Core (IgG anti-HBc) serological test will be performed. For HCV, an IgG-HCV test will be performed. For Chagas disease, strongyloidiasis and schistosomiasis, a serological test will also be performed. All of them will be processed in the reference laboratory facility of the PCC, being all of them based on the commercial tests available in each hospital of reference. Finally, for female genital mutilation, a gynaecological physical examination will be performed and/or referral to a gynaecologist will be carried out if required. A preventive protocol will be applied for girls at risk of this practice.

In the case of a positive test result or diagnosis, the individuals will be referred to receive specialized care as appropriate.

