1. JUSTIFICATION

Over 200 million girls and women worldwide are estimated to be living with the effects of female genital mutilation (FGM), which can cause several physical, mental and sexual health complications (1). Women who have undergone FGM often delay or do not seek help when they experience health problems that may be linked to the procedure because of several reasons, such as shame, lack of access or affordability, normalization of certain health-related symptoms, lack of confidence in healthcare providers (2). On the other hand, women who do seek care for particular medical problems may not be aware about the complications of FGM and therefore, they may not disclose their experience of FGM to the care provider (2).

Primary health care providers play an important role in supporting girls and women living with FGM, and improving their health and well-being (1). Providing care and treatment requires not only understanding women's needs at all levels but also providing adequate information so that they can make informed decisions (2). It is essential that healthcare providers communicate and discuss women's health and FGM status with them in a sensitive and non-judgmental manner, although this discussion can be challenging for both parts (2).

Within the framework of the ISMiHealth project, which contributes to the screening and detection of migrant women who have suffered FGM, the research team identified the need to further investigate the health needs of these women and their perceptions about the way FGM is currently approached in Spain. Relevant recommendations on how to address this topic and a training course for healthcare providers will be carried out by a group of experts.

This study intends to contribute towards the development of culturally sensitive screening methods of FGM that can be integrated into the ISMiHealth digital tool, so that healthcare providers can identify

those women who may have been victims of FGM and address their health needs. By improving the types of questions in the existing tool and the way they are structured and worded, this will allow practitioners to start talking about FGMs in a respectful and trustful manner with their patients.

BIBLIOGRAPHY

- 1. Person-centred communication for female genital mutilation prevention: a facilitator's guide for training health-care providers. Geneva: World Health Organization; 2022.

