Endpoint 6: The number of the screening tests performed for each individual condition will be compared between the intervention and control PCCs before and after the implementation.

Endpoint 7: Associations between the screening performance of the aggregated infections with different socio-demographic and epidemiological factors, such as, sex, age, geographic areas immunosuppression status, being attended in an intervention centre, fulfilling the screening criteria, among others, will be analysed.

Endpoint 8: Associations between the screening performance of each individual condition with different socio-demographic and epidemiological factors, such as, sex, age, geographic areas immunosuppression status, being attended in an intervention centre, fulfilling the screening criteria, among others, will be analysed.

Exploratory Endpoints

Endpoint 9: The number of migrant patients under follow-up in the hospital after a diagnosis of an infection or FGM will be estimated using the Minimum basic dataset (MBDS).

Endpoint 10: The number of migrant patients under treatment after a diagnosis will be estimated using the data from the EPR systems and MBDS.

Endpoint 11: The prevalence of each condition will be estimated using as the denominator the total number of tested migrant patients for that specific condition.

3. Study Methods

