5.1 Timing of Analyses

In the Catalan Institute of Health, data will be extracted retrospectively after the year of implementation from the EPR system (eCAP) by the Information Technology (IT) staff of the Sistema d'Informació per al Desenvolupament de la Investigació en Atenció Primària (SIDIAP). The study variables will be pseudo-anonymized, with technical and functional separation, by a SIDIAP data manager. SIDIAP will be responsible for the data processing in Catalonia. Regarding SIDIAP source data, the strict SIDIAP security standards will be followed.

In Andalusia, the data will be extracted retrospectively after the year of implementation by a specialized IT committee of the Andalusian Health Service Institution of the area involved in this project (Almería). The information will be extracted retrospectively and will include: 1) the check-list from the tool and 2) the demographic and clinical variables. Then, the IT committee will link this information with the laboratory data of the reference hospital (Hospital de Poniente in Almeria) and will pseudo-anonymize the data.

Thereafter, the biostatistician responsible for the data analysis will have access to the pseudo-anonymized data. The pseudo-anonymized data, which will be analysed after the year of intervention is completed, will include the variables detailed in Annex 1 for the targeted migrant population of the PCCs of Catalonia and Andalusia included in the study.

In any case, the data from the Catalonian centres will be analysed separately from data of the PCCs from Almeria where a process evaluation will be performed and only preliminary effectiveness data will be estimated.

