intervention level. Linear regressions will be performed for the monthly detection rates of the aggregated infections, and of each individual condition, comparing the intervention and control centres before and during the intervention period.

- Other secondary outcomes will be the proportion of screening tests performed for the aggregated infections and for each individual condition, and factors associated with having a higher screening performance. For this, associations with continuous variables will be evaluated using t-tests, or one-way analysis of variance (one-way ANOVA) for normally distributed quantitative variables, while for not normally distributed quantitative variables, Wilcoxon Rank-Sum and Kruskal-Wallis tests will be carried out. Pearson's chi-square test or Fisher's exact test will be performed to evaluate the associations between categorical variables. In addition, odds ratio (OR) will be estimated (Table 3). Mixed effects logistic regression models will be carried out to identify associations between the screening performance and socio-demographic and epidemiological characteristics, and adjusted odds ratio (aOR) will be estimated, using the region of the PCC as a random intercept (Table 3).
- **b.** The **prevalence** of each individual condition will be estimated and reported with its respective 95%CI. The prevalence for each infection was defined as the number of diagnoses identified by the screening tests performed among the people that were tested. Serology tests will be contemplated for HIV, HBV, HCV, *T.cruzi*, *S.stercoralis* and *Schistosoma spp.* infections; for active TB, chest radiographies will be examined; for FGM, the completed questionnaires and/or referrals to specialists will be considered.

See table 4 for details of the methodology employed for the outcomes.

Data analysis in Andalusia

A similar analysis approach will be carried out in Andalusia but the limited number of PCCs may prevent to estimate the health impact of the tool, therefore, we plan to estimate preliminary effectiveness data. In addition, the analysis for syphilis, latent TB and intestinal parasites will be executed. Nevertheless, because the pilot study will be conducted in six PCCs of one area (Almería), we won't be able to carry mixed-effects logistic regression models and instead, multiple logistic regressions will be performed.

7. Tables and Figures

Table 1. Description of the ISMiHealth sample.

| Variables | Summary statistics | | |

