| | FGM (completed | |
| | questionnaires) | |
| Associations with the scre | ening performance for all | Bivariate and multivariate |
| aggregated infections | | analysis |
| | HIV | |
| | Syphilis^ | |
| Associations with the | HBV | Bivariate and multivariate |
| screening performance | HCV | analysis |
| for each individual | active TB | |
| condition | latent TB^ | |
| | T.cruzi infections | |
| | S.stercoralis infections | |
| | Schistosoma spp. infections | |
| | Intestinal parasites^ | |
| | FGM | |
| Patients under follow-up a | after diagnosis | Bivariate analysis |
| Patients under treatment | after diagnosis | Bivariate analysis |
| Cured patients | | Bivariate analysis |
| | HIV | |
| | Syphilis^ | |
| | HBV | Numerator: number of |
| Prevalence of each | HCV | detected cases for each |
| condition | active TB | specific condition. |
| | latent TB^ | Denominator : number of |
| | T.cruzi infections | tested patients for each |
| | S.stercoralis infections | specific condition. |
| | Schistosoma spp. infections | |
| | Intestinal parasites^ | |
| | FGM | |

HIV: human immunodeficiency virus, HBV: hepatitis B virus, HCV: hepatitis C virus, TB: tuberculosis, FGM: female genital mutilation, TST: tuberculin skin test, IGRA: Interferon Gamma Release Assay; ^Only in the Andalusian site; The detection rate of all aggregated infections and the individual conditions will be calculated using the numbers of diagnoses per month over at least five years until the end of the intervention.

Figure 1. Flow chart of the migrant population

Figure 2. Monthly detection rates of the aggregated infections

Figure 3-9. Monthly detections of each individual condition (infections and FGM)

8. Reporting Conventions

Dates will be reported using the format MM/DD/YYYY. P-values will be reported to 3 decimal places. P-values less than 0.001 will be reported as '<0.001'. Statistics such as means, standard deviations, median values and percentages, will be calculated using the same decimal digits as the raw data. Rounding off will be performed on the final calculation value and reported according to publication requirements.

9. Technical Details

The data of the ISMiHealth study will be analysed with Stata Statistical Software: Release 16. At the time of the writing, the operating system of the computer that will be used for the analysis is Windows.

10. Summary of Changes to the Protocol

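### FGM screening in Endpoints 6 and 8 is counted only by completed questionnaires, a form that control centres may not have, so the between-arm comparison may show who holds the form and not who screens

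*SAP*

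**What the plan says.** - **Screening measure.** SAP Annex 1 defines the variable `fgm` as "Questionnaires completed for FGM" (yes/no). SAP Table 4 also lists completed questionnaires as the FGM screening test. For every other condition the test variable is a serology, chest radiograph, TST, IGRA or stool sample.
- **Use.** Endpoint 6 (SAP 2.3): "The number of the screening tests performed for each individual condition will be compared between the intervention and control PCCs before and after the implementation". Screening for each condition is also modelled in Endpoint 8, with attendance at an intervention centre among the factors.
- **Where FGM questions sit.** The FGM sub-study (Protocol Annex 5, section 1) hopes to help practitioners raise the subject "By improving the types of questions in the existing tool and the way they are structured and worded".
- **Control centres.** Under Protocol section 5 they receive training with the same recommendations but "will not initiate the tool/prompts onto the EPR system".
- **FGM procedure.** Protocol section 6, without distinguishing the arms: "a gynaecological physical examination will be performed and/or referral to a gynaecologist will be carried out if required". It names no questionnaire.
- **Detection.** Endpoint 2 identifies FGM cases by ICD code and/or gynaecologist referral.
- **Prevalence.** SAP section 6, Catalonia, item b: "for FGM, the completed questionnaires and/or referrals to specialists will be considered". Table 4 divides detected cases by tested patients.

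**The concern.** A laboratory test or radiograph leaves the same record whether or not a prompt led to it. A questionnaire leaves a record only where the form exists. If the form comes with the tool, the intervention also supplies the instrument that measures its own effect, and ascertainment differs by arm and by period. A control clinician who assesses FGM risk, examines or refers as the protocol describes would then count as not screening.

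At stake are the FGM comparison in Endpoint 6 and the FGM model in Endpoint 8, including the arm odds ratio in the FGM version of Table 3. A recording difference could be reported there as better screening. The FGM prevalence in Endpoint 11 has a related problem of definition: an ICD-coded case need not be a woman with a questionnaire.

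**Working it through.** The plan gives no expected FGM questionnaire count, no number of eligible women and no FGM screening rate. There is no figure to reproduce, so the check has two parts.

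**1. The FGM definitions side by side**

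| Use | Record counted | Can arise without the tool? |
|---|---|---|
| Protocol section 6, procedure | Examination and/or gynaecology referral | Yes |
| Endpoint 2, detection | ICD code and/or gynaecology referral | Yes |
| Endpoints 6 and 8 (Table 4, Annex 1), screening | Completed questionnaire only | Not stated |
| SAP section 6 item b, prevalence | Questionnaire and/or referral | Referral yes; questionnaire not stated |
| Table 4, prevalence denominator | Tested patients; the FGM test is the questionnaire | Not stated |

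Only the screening measure rests wholly on a record whose availability is unknown. On timing, Protocol section 5 says that Andalusia integrates the tool for the first time, so a tool-based form could not exist there before implementation. In Catalonia the prototype was tested in four centres (Protocol section 1).

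**2. How large the distortion could be**

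Assumptions, none from the documents: N eligible women per arm; the same true screening proportion p in both arms; full recording in the intervention arm; a share c recorded in the control arm; women independent, with clustering ignored. The SAP threshold is p<0.05, taken here as two-sided.

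*Control centres cannot record at all (c = 0).* Fisher's exact p for k against 0 is 2 × C(N,k)/C(2N,k), close to 2 × (1/2)^k. For k = 5 this is about 2 × 0.03125 = 0.0625. For k = 6 it is about 2 × 0.015625 = 0.03125; exact values are 0.0301, 0.0310 and 0.0312 for N = 200, 1000 and 5000. Six questionnaires against none is therefore already significant, and the odds ratio has no finite estimate.

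*Partial capture.* Apparent odds ratio = [p/(1−p)] / [cp/(1−cp)]. Probability of a significant result = Φ[(d − 1.96·SE0)/SE1], where d = p − cp, SE0 uses the pooled proportion and SE1 the separate ones.

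For N = 1000, p = 0.05, c = 0.5:
- d = 0.05 − 0.025 = 0.025; pooled proportion 0.0375.
- SE0 = √(2 × 0.0375 × 0.9625/1000) = 0.00850.
- SE1 = √[(0.05 × 0.95 + 0.025 × 0.975)/1000] = 0.00848.
- (0.025 − 1.96 × 0.00850)/0.00848 = 0.98, which gives Φ = 0.84.
- Odds ratio = 0.0526/0.0256 = 2.05.

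| True rate, both arms (N = 1000) | Control capture | Apparent OR | Chance of a false effect |
|---|---|---|---|
| 5% | half | 2.05 | 84% |
| 5% | quarter | 4.16 | >99% |
| 5% | none | not estimable | >99% |
| 2% | half | 2.02 | 45% |
| 2% | quarter | 4.06 | 86% |
| 2% | none | not estimable | >99% |
| either | full | 1.00 | 5% (nominal) |

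With N = 200 and half capture, the chance is 13% at a 2% rate and 26% at a 5% rate. Cluster-robust errors would generally lower these chances but would not move the apparent odds ratio. Everything turns on c, which the documents do not give.

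**The case against.** The strongest reply is that the documents never say that the SAP questionnaire belongs to the tool. The sub-study text speaks of questions, not of this variable. The main description of the tool in Protocol section 5 lists prompts and a check-list, and no FGM questionnaire. Catalan data are extracted from eCAP, which all Catalan Institute of Health centres share, and no separate tool extract is named for Catalonia. This stands: tool-only availability is an inference, and the illustration above depends on it.

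A reader might infer several stronger things that the documents do not support:
- **That control and pre-implementation counts are near zero by construction.** A form outside the tool is neither stated nor excluded.
- **That the tool's effect on FGM cannot be tested.** Endpoint 2 uses ICD codes and referrals, and Endpoint 5 lists no FGM questionnaire.
- **That FGM prevalence would be undefined or above 100% in control centres.** Prevalence by arm is not a planned estimate. SAP section 6 item b counts cases among those tested and admits referrals.
- **That the Andalusian check-list biases the test counts.** SAP 5.1 extracts "1) the check-list from the tool", but no endpoint is based on it.

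It is also fair to say that codes and referrals are detection records and cannot simply be renamed as screening. Annex 1 lists no coded FGM risk assessment and no examination field, and its referral variable covers only referrals that follow a diagnosis in the intervention period. The fix has to respect this.

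The reply does not remove the point. The questionnaire-only rule omits the procedures that the protocol names, differs from the SAP's own prevalence text, and leaves availability by arm and period unstated for a between-arm comparison.

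**Conclusion.** The point holds as a likely, unaddressed risk of differential ascertainment, confined to FGM in Endpoints 6 and 8, with an inconsistency in the FGM prevalence definition alongside it. The primary endpoint, FGM detection and the aggregated test count do not use the questionnaire.

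Its size cannot be fixed from the documents. It runs from no bias, if both arms record fully in both periods, to an odds ratio that cannot be estimated, if control centres have no form. The figures in between rest on assumed rates and assumed numbers of women, without clustering. The prevalence inconsistency does not depend on where the questionnaire sits. The change should be made before analysis; it does not bear on the trial's main conclusion.

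**What to change.** 1. State in SAP Annex 1 and Table 4 what the FGM questionnaire is, where it is completed, and whether it is available in each arm and each period.
2. Unless availability in both arms and both periods is confirmed, remove completed questionnaires from the between-arm FGM comparison in Endpoints 6 and 8. Report them only as a process measure of tool use in intervention centres.
3. Base any between-arm FGM conclusion on records that exist in both arms: FGM ICD codes and/or gynaecology referrals, as in Endpoint 2. Label this as detection, not screening. Extend the referral extraction to the pre-implementation period.
4. If the questionnaire is confirmed for all centres, count questionnaires and/or referrals as FGM screening, matching SAP section 6 item b.
5. Reconcile the FGM numerator and denominator in Table 4 with that item, so that cases are counted only among women counted as assessed. Say whether a referral alone makes a woman assessed, a case, or both; if both, every such woman is a case by definition and prevalence is pushed upwards.

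The cost is mainly SAP wording, plus some added data extraction for earlier referrals. The FGM screening count in intervention centres would be lower, or would drop out of the comparison.
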